#### Relapse:

Relapse following CR/CRi is defined as:

Peripheral Blood Counts-Reappearance of blasts in the blood that persist and are not considered to be due to count or marrow recovery.

Bone Marrow Aspirate and Biopsy-Presence of  $\geq 5\%$  blasts, not attributable to another cause (e.g., bone marrow regeneration).If there are no circulating blasts and the bone marrow contains 5% to 20% blasts, and if unclear if increase in the blasts is due to regeneration, reactive process or leukemia, then a repeat bone marrow performed  $\geq 1$  week later documenting  $\geq 5\%$  blasts is necessary to meet the criteria for relapse.

Molecular Relapse (after CRMRD-): If studied pre-treatment, reoccurrence of MRD as assessed by quantitative RTqPCR or by multi-color flow cytometry. Sensitivities vary by marker tested, and by method used. Since this study does not use centralized laboratory, MRD status will be recorded but clinical relapse parameters will be used for survival endpoint assessment.

#### Progression after Hematologic Improvement

One or more of the following: a 50% or greater decrement from maximum response levels in granulocytes or platelets, a reduction in hemoglobin concentration by at least 2 g/dL, or transfusion dependence not due to other toxicities and bone marrow blasts  $\geq 5\%$ .

#### **7.1.2.7 Tumor Tissue Collection and Correlative Studies Blood Sampling**

Tumor tissue collection and blood collection will be performed as the Trial Flow Chart and processed as detailed in in the Appendix 11.5.

#### **7.1.3 Laboratory Procedures/Assessments**

Details regarding specific laboratory procedures/assessments to be performed in this trial are provided in Trial Flow Chart and below in Laboratory Safety Evaluations (Hematology, Chemistry and Urinalysis)

Laboratory tests for hematology, chemistry, urinalysis, and others are specified in Table 7.

Table 7. Laboratory Tests

Hematology	Chemistry	Urinalysis	Other
Hematocrit	Albumin	Blood	Serum $\beta$ -human chorionic gonadotropin†
Hemoglobin	Alkaline phosphatase	Glucose	( $\beta$ -hCG)†
Platelet count	Alanine aminotransferase (ALT)	Protein	PT (INR)
WBC (total and differential)	Aspartate aminotransferase (AST)	Specific gravity	aPTT, fibrinogen
Red Blood Cell Count	Lactate dehydrogenase (LDH)	Microscopic exam ( If abnormal )	Total triiodothyronine (T3)
Absolute Neutrophil Count	Carbon Dioxide ‡	results are noted	Free tyroxine (T4)
Absolute Lymphocyte Count	( $CO_2$ or bicarbonate)	Urine pregnancy test †	Thyroid stimulating hormone (TSH)
	Uric Acid		PK
	Calcium		
	Chloride		Blood for correlative studies
	Glucose		
	Phosphorus		
	Potassium		
	Sodium		
	Magnesium		
	Total Bilirubin		
	Direct Bilirubin ( If total bilirubin is elevated above the upper limit of normal )		
	Total protein		
	Blood Urea Nitrogen		

† Perform on women of childbearing potential only. If urine pregnancy results cannot be confirmed as negative, a serum pregnancy test will be required.

‡ If considered standard of care in your region.

Laboratory tests for screening or entry should be performed within 14 days prior to the first dose of treatment. However, repeat laboratory tests are required within 72 hours prior to the first dose of treatment in Cycle 1. After Cycle 1, pre-dose laboratory procedures can be conducted up to 72 hours prior to dosing. Results must be reviewed by the investigator or qualified designee and found to be acceptable prior to each dose of trial treatment.

### **7.1.3.1 Pharmacokinetic/Pharmacodynamic Evaluations**

#### **7.1.3.1.1 Blood Collection for Serum Pembrolizumab- N/A**

#### **7.1.3.1.2 Blood Collection for Anti-Pembrolizumab Antibodies- N/A**

#### **7.1.3.1.3 Correlative Studies Procedures (Exploratory Biomarkers)**

Samples will be immediately processed following our Standard Operating Procedure (Appendix 11.4) in the laboratory of [name]. Participating institutions will have an option to process specimens locally and batch ship or to ship specimens within 24 hours of collection to the laboratory of [name].

The pharmacodynamics of azacitidine and pembrolizumab treatment will be assessed by examining (quantifying) biomarkers in peripheral blood and bone marrow (tumor tissue). Additional biomarkers may be analyzed in peripheral blood and tumor tissue collected prior to and after initiation of therapy in order to identify markers that may predict response to treatment. The proposed studies will be done in collaboration with Univ of North Carolina. Detailed schedules of pharmacodynamic evaluations are provided in Trial Flow Chart Section 6.0.

##### **7.1.3.1.3.1 Flow Cytometry Studies**

We will perform multi-color flow cytometry on PB and BM specimens before and after AZA and AZA/pembrolizumab treatment using three pre-determined panels of mAbs including but not limited to those specific for CD3, CD4, CD8, PD-1, CD45RA, CCR7, CD27, CD28, Ki-67, T-bet, CD127, CD25, FoxP3, HLA-DR, CTLA-4, TNFRII, ICOS, TIM3, LAG-3, CD160, 2B4, BTLA, KLRG-1, CD16, CD14, and CD56. This multi-color approach allows phenotypic separation of human CD4+FoxP3+ T cells into three distinct subpopulations as well as assessment of their proliferative status (% Ki-67 positive cells). The expression of HLA-DR, TNFRII and ICOS will be measured to characterize their activation status. The expression of co-inhibitory molecules (PD-1, TIM3, LAG-3, CD160, 2B4, BTLA, KLRG-1) will also be examined in relation to different CD4+ and CD8+ T cell subpopulations (expressing CD45RA, CCR7, CD27, and CD28). This panel will be combined with assessment of effector cytokines (IL-2, IFN- $\gamma$ , IL-17) or canonical transcription factors (T-bet, Eomes, Blimp-1). Additionally, natural killer cells (NK), NK-T cells, and myeloid- derived suppressor cells (MDSCs) will be enumerated using the following gating strategies: CD14+HLA-DRneg/low (MDSCs); CD16 and CD56 (NK/NK-T cells). We will also use a highly multiplexed flow cytometry panels to analyze expression of co-inhibitory molecules ligands (PD-L1, PD-L2, galectin-9, CD80,

CD86) on MDSCs, leukemia blasts, and leukemia stem cells. We will analyze three distinct AML subpopulations defined as CD33+CD117+CD14 (AML progenitors) CD33+CD117+CD14 (AML myelo/monoblasts), CD33+CD117+CD14+ (AML promonocytes) and CD34+CD38ALDHintermediate (leukemia stem cells), when feasible. Our group has extensive experience in characterizing immune recovery in AML patients during and after chemotherapy and allo-SCT.

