## 1.0 TRIAL SUMMARY

Abbreviated Title	Azacitidine and Pembrolizumab for the treatment of relapsed/refractory AML patients and newly diagnosed older ( $\geq 65$ years) AML patients who are not candidates for intensive induction chemotherapy
Trial Phase	Phase II
Clinical Indication	Safety Run In Phase (only Cohort 1): The treatment of relapsed and refractory AML patients with no prior history of allogeneic hematopoietic stem cell transplant (HSCT).  Phase 2: Cohort 1: The treatment of relapsed and refractory AML patients. Cohort 2: The treatment of newly diagnosed AML patients ( $\geq 65$ years) who are not candidates for intensive induction chemotherapy.
Trial Type	Interventional
Type of control	No control arm
Route of administration	Intravenous pembrolizumab; intravenous or subcutaneous azacitidine
Trial Blinding	Open Label
Treatment Groups	Cohort 1: Relapsed/refractory AML patients  Cohort 2: Newly diagnosed older patients ( $\geq 65$ years) who are not candidates for intensive induction chemotherapy
Number of trial subjects	Cohort 1: 10-40  Cohort 2: 10-40
Estimated enrollment period	24 months
Estimated duration of trial	48 months
Duration of Participation	Each subject will participate in the trial from the time the subject signs the Informed Consent Form through the final protocol-specified contact. Each treatment cycle will last 28 days. Bone marrow will be examined after 2 and 6 cycles and every 3-6 months thereafter. Patients who achieved complete remission (CR/CRI) or patients without remission but benefiting from therapy (partial remission [PR], morphologic leukemia-free state [MLFS], hematologic improvement [HI], stable disease [SD]) can continue on study receiving both azacitidine and pembrolizumab as long as they have ongoing clinical benefit without evidence of significant toxicity or disease progression and up to 2 years.
Estimated average length of treatment per patient	Up to 2 years or as long as subjects have ongoing clinical benefit without evidence of disease progression or significant toxicity.

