well as subsets of macrophages and dendritic cells. The ligands for PD-1 (PD-L1 and PD-L2) are constitutively expressed or can be induced in a variety of cell types, including non-hematopoietic tissues as well as in various tumors. Both ligands are type I transmembrane receptors containing both IgV- and IgC-like domains in the extracellular region and contain short cytoplasmic regions with no known signaling motifs. Binding of either PD-1 ligand to PD-1 inhibits T-cell activation triggered through the T-cell receptor. PD-L1 is expressed at low levels on various non-hematopoietic tissues, most notably on vascular endothelium, whereas PD-L2 protein is only detectably expressed on antigen-presenting cells found in lymphoid tissue or chronic inflammatory environments. PD-L2 is thought to control immune T-cell activation in lymphoid organs, whereas PD-L1 serves to dampen unwarranted T-cell function in peripheral tissues. Although healthy organs express little (if any) PD-L1, a variety of cancers were demonstrated to express abundant levels of this T-cell inhibitor. PD-1 has been suggested to regulate tumor-specific T-cell expansion in subjects with melanoma (MEL). This suggests that the PD-1/PD-L1 pathway plays a critical role in tumor immune evasion and should be considered as an attractive target for therapeutic intervention.

Pembrolizumab is a potent and highly selective humanized monoclonal antibody (mAb) of the IgG4/kappa isotype designed to directly block the interaction between PD-1 and its ligands, PD-L1 and PD-L2. Keytruda™ (pembrolizumab) has recently been approved in the United States for the treatment of patients with unresectable or metastatic melanoma and disease progression following ipilimumab and, if BRAF V600 mutation positive, a BRAF inhibitor.

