#### **4.2.2 Rationale for Dose Selection/Regimen/Modification**

An open-label Phase I trial (Protocol 001/NCT01295827) was conducted to evaluate the safety and clinical activity of single agent MK-3475. The dose escalation portion of this trial evaluated three dose levels, 1 mg/kg, 3 mg/kg, and 10 mg/kg, administered every 2 weeks (Q2W) in subjects with advanced solid tumors. All three dose levels were well tolerated and no dose-limiting toxicities were observed. This first in human study of MK-3475 showed evidence of target engagement and objective evidence of tumor size reduction at all dose levels (1 mg/kg, 3 mg/kg and 10 mg/kg Q2W). No MTD has been identified to date. 10.0 mg/kg Q2W, the highest dose tested in PN001, is the dose and schedule utilized in a Phase IB trial (Protocol 013/ NCT01953692) in patients with hematologic malignancies (including MDS) to test for initial tumor activity. Recent data from other clinical studies within the MK-3475 program has shown that a lower dose of MK-3475 and a less frequent schedule may be sufficient for target engagement and clinical activity.

PK data analysis of MK-3475 administered Q2W and Q3W showed slow systemic clearance, limited volume of distribution, and a long half-life (refer to IB). Pharmacodynamic data (IL-2 release assay) suggested that peripheral target engagement is durable (>21 days). This early PK and pharmacodynamic data provides scientific rationale for testing a Q2W and Q3W dosing schedule.

A population pharmacokinetic analysis has been performed using serum concentration time data from 476 patients. Within the resulting population PK model, clearance and volume parameters of MK-3475 were found to be dependent on body weight. The relationship between clearance and body weight, with an allometric exponent of 0.59, is within the range observed for other antibodies and would support both body weight normalized dosing or a fixed dose across all body weights. MK-3475 has been found to have a wide therapeutic range based on the melanoma indication. The differences in exposure for a 200 mg fixed dose regimen relative to a 2 mg/kg Q3W body weight based regimen are anticipated to remain well within the established exposure margins of 0.5 – 5.0 for MK-3475 in the melanoma indication. The exposure margins are based on the notion of similar efficacy and safety in melanoma at 10 mg/kg Q3W vs. the proposed dose regimen of 2 mg/kg Q3W (i.e. 5-fold higher dose and

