Uric Acid, Phosphate, Magnesium, LDH		X	X		X	X	X	X c	X c	X	X	X		
T3, FT4 and TSH		X				X i								
Urinalysis		X												
Efficacy Measurements														
Bone Marrow Aspirate/Biopsy d,f		X d,f				X d,f				X d,f	X d,f	X d,f		
Tumor Biopsies/Archival Tissue Collection/Correlative Studies Blood														
Correlative Studies Peripheral Blood Collection		X e	X e		X e	X e	X e			X e		X e		

Trial Period:	Screening Phase	Treatment Cycles								End of Treatment			Post-Treatment
		To be repeated beyond Cycle 3				C1 and C2 D15, D22	C3 D1	C3 D2-7	C3 D15	C3 D22			
Treatment Cycle/Title:	Main Study Screening	C1 and C2 D1	C1 and C2 D2-7	C1 D8	Survival Follow-Up								
Scheduling Window (Days):	-14 to -1	±3	± 3	± 3	± 3	± 3	± 3	± 3	± 3	At time of Discontinuation	30 days post discon (± 4 days)	Every 8 weeks post discon j	Every 12 weeks
Correlative Studies Bone Marrow Collection	X d,f				X d,f				X d,f	X d,f		X d,f	

a Azacitidine should be administered without interruption in each cycle. Pembrolizumab to be administered starting on day 8 cycle 1 every 3 weeks. (See Section 5.2.1.4., 5.2.1.5, and 5.2.1.5.1 for specific exceptions)

bDuring cycle 1 and 2, patients will be seen weekly. In subsequent cycles, the frequency of study required visits will be reduced to d1 prior to azacitidine and prior to each pembrolizumab administration. However, patients may be seen more frequently as needed according to standard of care for management of patients with AML as determined and at the discretion of investigator/treating physician.

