### **8.2.5 Analysis of Correlative Endpoints**

We will perform multi-color flow cytometry on PB and BM specimens before and after AZA and AZA/pembrolizumab treatment using three pre-determined panels of mAbs including but not limited to those specific for CD3, CD4, CD8, PD-1, CD45RA, CCR7, CD27, CD28, Ki-67, T-bet, CD127, CD25, FoxP3, HLA-DR, CTLA-4, TNFRII, ICOS, TIM3, LAG-3, CD160, 2B4, BTLA, KLRG-1, CD16, CD14, and CD56. The analyses of pre- and post-treatment PB and BM specimens for immune parameters will be descriptive and graphical in nature. Data will be summarized for each cohort separately. The change in flow values at each time point after AZA and AZA/pembrolizumab relative to the baseline value will be checked for skewness and log-transformed as appropriate. The changes will be modeled using mixed-effects, linear regression models that included fixed effects for time and a random effect for the patient to account for within-patient correlation of measurements. To explore potential differences in the change in flow values across patient subgroups, interaction terms will be included in the regression models. Post-treatment PD changes in gene expression and methylation in immune gene signaling circuits in tumor biopsies and PB will be summarized with descriptive statistics and correlated with clinical outcomes.

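### On-treatment PD-1 staining after cycle 1 day 8 is analysed as change in expression, although the drug may be covering the stained molecule and the plan has no rule to tell the two apart

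*Combined protocol and SAP*

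**What the plan says.** Section 7.1.3.1.3.1 plans "multi-color flow cytometry on PB and BM specimens before and after AZA and AZA/pembrolizumab treatment". The antibody panels for this work include PD-1 and are listed by target only. Within the T-cell work, "The expression of co-inhibitory molecules (PD-1, TIM3, LAG-3, CD160, 2B4, BTLA, KLRG-1) will also be examined" across CD4 and CD8 subpopulations.

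Section 8.2.5 takes "The change in flow values at each time point after AZA and AZA/pembrolizumab relative to the baseline value", checks it for skewness, and fits a linear mixed model with time as a fixed effect and a per-patient random effect. Subgroup differences are explored through interactions. There is no provision for a stained target that is also the drug's target, and no term for time since dosing.

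Section 4.1.1.1 describes pembrolizumab as an antibody "designed to directly block the interaction between PD-1 and its ligands, PD-L1 and PD-L2". Section 4.2.2 reports that an IL-2 release assay "suggested that peripheral target engagement is durable (>21 days" after dosing. Footnote a of the flow chart (Section 6.1) reads: "Pembrolizumab to be administered starting on day 8 cycle 1 every 3 weeks". Research blood is drawn before dosing on C1D1, C1D8, C2D1 and C2D22, then on day 1 of every second cycle from cycle 3, and at follow-up visits. Serum pembrolizumab is marked not applicable (Section 7.1.3.1.1).

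**The concern.** A labelled antibody that competes with pembrolizumab reads drug-bound PD-1 as absent. The baseline and on-treatment values would then measure different things: total surface PD-1 before the drug, and only the unoccupied part afterwards. The modelled change would mix any change in expression with blocking of the stain.

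This matters because PD-1-expressing T cells carry the mechanistic hypothesis in Sections 4.2.1 and 4.2.3.2, which expect azacitidine to raise co-signalling molecules. Masking pushes the other way. Section 4.2.2 also reports that in some patients the PD-1 locus regains methylation towards the start of the next cycle. C2D1 sits at that point, so a masked fall there could be taken for the expected biology.

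With a competing stain, the artefact would also follow dosing history. Patients whose pembrolizumab was held could appear to have more PD-1 than patients on schedule, and a subgroup interaction could pick that up as a difference between patients.

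**Working it through.** **Inputs.** "Each treatment cycle will last 28 days" (Section 1.0). Pembrolizumab every 21 days from C1D8, and the blood-draw days (Section 6.1 and its footnotes). Suggested engagement of more than 21 days (Section 4.2.2).

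**Step 1: the calendar.** Study day = 28 × (cycle − 1) + day. Doses fall on day 8 + 21k, with k = 0, 1, 2, …: days 8, 29, 50, 71, 92, 113 and so on. The flow chart's blood-sample footnote treats C1D8 and C2D22 as pembrolizumab days. These are day 8 and day 28 + 22 = 50, both in the list, so the plan's schedule is reproduced.

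**Step 2: days since the last prior dose.**

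| Sample | Study day | Last prior dose | Gap (days) |
|---|---|---|---|
| C1D1 | 1 | none | – |
| C1D8 (pre-dose) | 8 | none | – |
| C2D1 | 29 | 8 | 21 |
| C2D22 | 50 | 29 | 21 |
| C3D1 | 57 | 50 | 7 |
| C5D1 | 113 | 92 | 21 |
| C7D1 | 169 | 155 | 14 |
| C9D1 | 225 | 218 | 7 |

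From C5 the samples are 56 days apart. Since 3 × 56 = 168 = 8 × 21, the pattern 21, 14, 7 repeats. Every scheduled on-treatment gap after C1D8 is therefore 7 to 21 days. These are nominal: with the ±3-day visit window, a 21-day gap could reach 21 + 3 + 3 = 27 days, where the engagement statement neither confirms nor excludes occupancy.

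**Step 3: size of the effect if the stain competes.** A simple proportional model:

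apparent change = (1 + true change) × (1 − occupancy × competition) − 1

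Occupancy and competition are not in the documents. Assume occupancy of 70% to 95%, and competition of 0, 0.5 or 1.

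- No true change, competition 0: 0%.
- No true change, competition 0.5: 1 − 0.70 × 0.5 = 0.65, so −35%; 1 − 0.95 × 0.5 = 0.525, so −47.5%.
- No true change, competition 1: −70% to −95%, reaching −100% at full occupancy.
- True rise of 50%, competition 1: 1.5 × 0.30 − 1 = −55%; 1.5 × 0.05 − 1 = −92.5%. The sign is reversed.

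**Step 4: samples outside this reasoning.**

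- Follow-up blood comes every 8 weeks after discontinuation (8 × 7 = 56 days, ±14), and follow-up marrow every 4 to 6 months (Section 7.1.5.4).
- Table 5 allows pembrolizumab at 4- or 6-week intervals, so a pre-dose gap can be 28 or 42 days.
- Table 4 allows doses to be withheld, and Section 5.2.1.2 lets a patient continue on one agent.
- Marrow after cycle 2 follows the C2D22 dose by roughly a week (day 57 − day 50 = 7), but the engagement evidence is peripheral.

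The documents give no occupancy for any of these.

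**The case against.** **Whether masking happens at all is unknown.** This stands. The panels are fixed in advance, the clone is not named in the protocol, and Appendix 11.4 defers specimen details to a Laboratory Manual that is not among the documents. A non-competing clone may already be in use. The range of 0% to about −100% expresses that uncertainty and is not an estimate.

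**The engagement evidence is limited.** This also stands. Section 4.2.2 relies on a functional assay in blood, says only that the data suggest durability, and gives no occupancy fraction.

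**A reader might infer that every sample after C1D8 is drug-occupied.** The documents do not support that. Follow-up, held-dose and stretched-interval samples exist, and marrow occupancy is not addressed.

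**A reader might also infer that masking would empty PD-1-positive gates used for cytokine or activation readouts.** Section 7.1.3.1.3.1 specifies no such gate. PD-1 is one of seven co-inhibitory markers examined across subpopulations defined by other markers, and the activation markers are described for the FoxP3-positive CD4 cells.

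**The azacitidine hypothesis is tested before the drug, and PD-1 mRNA and promoter methylation are already planned.** Both are true. C1D1 against C1D8 is free of pembrolizumab, and Section 7.1.3.1.3.3 supplies readouts that drug binding cannot mask. But Section 8.2.5 still models the later flow values as change from baseline and does not link their reading to the mRNA.

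**The endpoint is exploratory and largely descriptive.** This stands, and it limits the importance of the point.

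**Conclusion.** The point holds for scheduled on-treatment blood after C1D8 on an uninterrupted schedule. Those draws fall a nominal 7 to 21 days after a dose, within the suggested engagement period, and Section 8.2.5 does not separate lower expression from a blocked stain. If the detection antibody competes with pembrolizumab, a post-pembrolizumab fall in PD-1 protein cannot be read as biology, and on the assumed values even a true 50% rise could appear as a fall of 55% to 92.5%. If it does not compete, there is no bias.

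The documents do not show that masking occurs, that it reaches marrow, or that it persists into follow-up or through held or stretched dosing. The C1D1 versus C1D8 contrast, the CR/CRi analysis, the sample size and the stopping rules are untouched. This is an inexpensive improvement to an exploratory analysis.

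**What to change.** Add to Section 8.2.5:

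- Change in PD-1 surface protein is interpreted as expression only for samples drawn before any pembrolizumab (baseline and C1D8), unless the laboratory documents that pembrolizumab does not block its PD-1 stain.
- If that is not documented, later PD-1 staining is reported as available (unoccupied) PD-1, alongside days since the last pembrolizumab dose. On-treatment expression is taken from the PD-1 mRNA already planned in Section 7.1.3.1.3.3.

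One way to document it is to incubate stored baseline cells with pembrolizumab before staining and compare them with untreated cells from the same sample. Appendix 11.4 already provides for viable frozen cells.

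The cost is some SAP wording and one bench check. The downside is that, if the antibody competes, there is no PD-1 protein expression trend after C1D8. Later samples, including those in follow-up, are still reported, but as available PD-1.
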